# MODIFICATION HISTORY

Unique Identifier for this Version	Date of the Document Version	Author	Significant Changes from Previous Authorized Version
1.0	22AUG2024	PPD	Not Applicable – First Version

## 1. Introduction

This statistical analysis plan (SAP) describes the rules and conventions to be used in the presentation and analysis of safety, pharmacokinetics, and pharmacodynamic data for Protocol VIS954-101. It describes the data to be summarized and analyzed, including specifics of the statistical analyses to be performed.

This SAP is based on protocol version 1.0, dated 07Sep2023 and amendment 1 dated 20Oct2023.

# 2. STUDY OBJECTIVES AND ENDPOINTS

[figure not shown]
# 2.1. Primary Objective and Endpoints

Objectives	Endpoints
Primary:  To evaluate the safety and tolerability of VIS954 in healthy participants	Primary: Safety The following safety variables will be assessed: Incidence of TEAEs Physical examinations Vital sign measurements (blood pressure, pulse, body temperature, and respiratory rate)  12-Lead ECGs Clinical safety laboratory tests (hematology, clinical chemistry, coagulation, and urinalysis) Injection site reactions and Wong-Baker FACES Pain Rating Scale

ECG = electrocardiogram; TEAEs = treatment-emergent adverse events.

# 2.2. Secondary Objectives and Endpoints

Objectives	Endpoints	
Secondary:	Secondary:	
To assess the PK profile of	Pharmacokinetics	
	The following PK parameters for VIS954 will be determined, as	

Statistical Analysis Plan

Page 12 of 42

Objectives	Endpoints	
VIS954	appropriate:	
	• C max	
	• t max	
	AUC 0-inf	
	AUC 0-last	
	• t 1/2	
	V d /F	
	CL/F	
	Pharmacodynamics	
To determine the PD effect of VIS954	To characterize VIS954 C5aR1 RO (VIS954 binding)	
¥10757		

AUC0-inf = area under the concentration-time curve from predose extrapolated to infinite time; AUC0-last = area under the concentration-time curve from predose to the last quantifiable concentration; CL/F = apparent clearance; Cmax = maximum serum concentration; RO = receptor occupancy; t1/2 = apparent terminal elimination half-life; tmax = time of maximum serum concentration; Vd/F = apparent volume of distribution.

# 2.3. Exploratory Objectives and Endpoints

Statistical Analysis Plan

# 3. STUDY DESIGN

# 3.1. General Description

This is a phase 1, randomized, placebo-controlled, double-blind, single ascending dose, first-in-human (FIH) study to assess the safety, tolerability, PK, and PD of VIS954 administered subcutaneously (SC) in healthy participants.

The study will be conducted in 6 sequential cohorts. Each cohort will enroll 9 participants, randomized to VIS954 or placebo at a ratio of 7:2 (7 VIS954:2 placebo). Eligible participants will be centrally assigned to randomized study intervention. Before the study is initiated, information and directions for the randomization will be provided to the trial site unblinded pharmacist. Each cohort will also optimally enroll 5 non-Japanese participants and 4 Japanese participants (achievement of this ratio is desired but not mandatory to advance to the next cohort). No more than one Japanese participant per cohort may be randomized to receive placebo.

Sentinel participants will be utilized in each cohort; the first 2 non-Japanese participants in each cohort will be randomized to receive either VIS954 (n = 1) or placebo (n = 1) and will receive the study intervention at least 24 hours before the remaining 7 participants in the cohort are dosed. The safety data from each of the 2 sentinel participants will be reviewed over the 24-hour post-administration period to determine whether it is appropriate to proceed with dosing of the remaining participants in the cohort as planned. A similar review will occur for each dose escalation. The remaining 7 participants in a cohort will be randomized to receive VIS954 (n = 6) or placebo (n = 1).

Escalation to next dosing level will occur after review of blinded safety data when at least 7 participants have completed  $\geq$  14 days in a cohort.

The planned dose of VIS954 for each cohort is summarized in Table A below. For more information, refer to Section 4.1 of the clinical study protocol.

Page 14 of 42

Statistical Analysis Plan

Table A: Planned dose of VIS954 for each cohort

Study Intervention for Each Cohort		
Cohort	Study Intervention	
Cohort 1	VIS954 or placebo	
Cohort 2	VIS954 or placebo	
Cohort 3	VIS954 or placebo	
Cohort 4	VIS954 or placebo	
Cohort 5	VIS954 or placebo	
Cohort 6	VIS954 or placebo	

### 3.2. Schedule of Events

Schedule of events can be found in Section 1.3 of the protocol.

# 3.3. Changes to Analysis from Protocol

The following changes to analysis from the protocol are included in this document:

Section 9.2.7.1 of the protocol states that disposition data will be presented based on all participants
randomized. But Section 5.3 of the protocol says minimal information for screen failure participants will
be collected. Therefore, this document outlines the disposition table and the corresponding listing to be
based on all participants who provided informed consent.

•	CCI

Visterra Insert
Customer Name/ Logo
Protocol VIS954-101
Page 15 of 42

Statistical Analysis Plan

# 4. PLANNED ANALYSES

The following analyses will be performed for this study:

- Analyses for Safety Monitoring Committee (SMC) meetings after at least 7 participants have completed
   ≥ 14 days in a cohort. IQVIA Biostatistics will not generate any listings or summaries for SMC meetings.
- Interim analysis summaries of data may be utilized by unblinded members of the sponsor (as described in the operations manual) for various reporting and future study planning purposes at any time prior to full database lock.
- Blinded dry-run analysis prior to database lock in preparation of the final analysis.
- Final analysis post database lock.

# 4.1. Safety Monitoring Committee

Reporting for the SMC will be handled by the study clinic and operations team and is outside the scope of this document.

# 4.2. Interim Analysis

When at least 7 participants have completed  $\geq$  14 days in a cohort, a review of the safety data will be performed by the SMC to authorize opening of the next cohort. As mentioned in Section 4.1, reporting for the SMC is outside the scope of this document. Additionally, interim summaries of data may be utilized by unblinded members of the sponsor (as described in the operations manual) for various reporting and future study planning purposes at any time prior to full database lock.

# 4.3. Final Analysis

All final, planned analyses identified in this SAP will be performed by IQVIA Biostatistics following sponsor authorization of the SAP, identification of major protocol deviations requiring analysis exclusions, database lock, determination of analysis set exclusions, and unblinding of treatment.

Dry run analysis will be completed prior to the database lock, with the purpose of setting up all

programming deliverables using interim data transfers, in advance of the commencement of final analysis post database lock.

### 5. ANALYSIS SETS

Agreement and authorization of participants included/excluded from each analysis set will be conducted prior to the database lock and unblinding of the study.

# 5.1. Process for Analysis Set Assignment

The list of protocol deviations will be reviewed periodically during the study conduct and its impact on the inclusion of participants in the various analysis sets defined subsequently in this section will be assessed by the relevant members of the study team and documented.

# 5.2. Screened Analysis Set [SCR]

The screened analysis set (SCR) will contain all participants who provide informed consent for this study. Participants in this population will be used for disposition listings and summaries.

# 5.3. Randomized Analysis Set [RND]

The randomized analysis set will contain all participants who pass all eligibility criteria and are randomized to study treatment assignment.

# 5.4. Safety Analysis Set [SAF]

The safety analysis set (SAF) will contain all participants who receive study medication (active or placebo), and participants will be classified according to treatment received.

# 5.5. Pharmacokinetic Analysis Set [PKAS]

The pharmacokinetic analysis set (PKAS) will consist of all participants who receive active study drug

Visterra Insert
Customer Name/ Logo
Protocol VIS954-101
Page 17 of 42

Statistical Analysis Plan

(VIS954) and have at least 1 measured post-dose VIS954 serum concentration at a scheduled PK time after start of dosing for at least 1 PK analyte without protocol deviations or events with potential to affect the evaluation of the PK data. Participants in this population will be used for all PK analyses.

# 5.6. Pharmacodynamic Analysis Set [PDAS]

The pharmacodynamic analysis set (PDAS) will contain all participants who receive study medication (active or placebo) and have at least 1 measured PD value at a scheduled time point after start of dosing. Participants in this population will be used for all PD analyses.

### 6. GENERAL CONSIDERATIONS

Derivation of the PK parameters for VIS954 in serum will be the responsibility of the clinical pharmacokineticist at IQVIA. The PK, PD, CCI and and safety summaries, data listings and figures as well as the statistical analysis of the related variables will be the responsibility of the study biostatistician at IQVIA.

## 6.1. Summary Statistics

For qualitative variables, the population size (N for sample size and n for available data) and the percentage (of available data) for each class of the variable will be presented. Quantitative safety variables will be summarized using descriptive statistics, including the population size (N for sample size and n for available data), mean, standard deviation (SD), 95% confidence interval (CI), median, minimum, and maximum values. Descriptive statistics will be presented similarly for PK, PD, CCI related quantitative variables with coefficient of variation expressed as a percentage (CV%) in place of

Visterra Insert
Customer Name/ Logo
Protocol VIS954-101
Page 18 of 42

Statistical Analysis Plan

95% CI. Geometric mean, and geometric CV% (GCV%) will be included for PK parameters, where applicable. Quartiles will be included for CCI variables, where appropriate. CV% will not be presented for change from baseline results.

#### 6.2. Treatment Summarization

In general, data will be presented and analyzed for each treatment group, for all VIS954 treated participants, and with placebo participants from all cohorts pooled into a single, overall placebo group. Data for Japanese and non-Japanese participants by treatment and overall, and all study participants will also be presented when appropriate. Participants will be analyzed according to the treatment they receive, instead of the planned (randomized) treatment.

For PK variables, the data will also be further summarized by Japanese and non-Japanese participants i.e., in addition to summarizing the PK variables by treatment group, the data will also be summarized stratified by non-Japanese participants and Japanese participants within each treatment group.

#### 6.3. Precision

Safety variables i.e., clinical laboratory values, vital signs, electrocardiogram (ECG) intervals, and Wong-Baker FACES Pain Rating, including derivations thereof, such as change from baseline, will be reported to the same precision as the source data.

All PK concentrations, PD, CCI results will be reported and analyzed with the same precision as the source data provided by the bioanalytical laboratory [PK CCI data from ICON lab and PD (receptor occupancy) from BioAgyltix] regardless of how many significant figures or decimals the data carry. Derived PK parameters will be rounded for reporting purposes in by-participant listings. The rounded derived PK data will be considered the source data for the calculation of descriptive statistics and the statistical analysis. For most derived PK parameters, 3 significant digits will be used as the standard rounding procedure, with the following exceptions:

- Parameters directly derived from source data (e.g., Cmax) will be reported and analyzed with the same precision as the source data.
- Parameters derived from actual elapsed sample collection times (e.g., tmax) will be reported with the

Page 19 of 42

Statistical Analysis Plan

same precision as the actual elapsed sampling time value of the source data.

For the reporting of descriptive statistics, the mean (arithmetic or geometric), SD, and CIs will be presented to one digit more precision than the source data. The minimum, median, and maximum will be presented to the same precision as the source data. CV% will always be reported to 1 decimal place.

# 6.4. Reference Start Date and Study Day

Study Day will be calculated from the reference start date and will be used to show start/stop day of assessments and events. It will appear in every listing where an assessment date or event date appears. Reference start date is defined as the day of study medication administration (Day 1 is the day of the study medication administration).

- If the date of the event is on or after the reference date, then:
- Study Day = (date of event reference date) + 1.
- If the date of the event is prior to the reference date, then:
   Study Day = (date of event reference date).

In the situation where the event date is partial or missing, the date will appear partial or missing in the listings, and Study Day, and any corresponding durations will be presented based on the imputations specified in APPENDIX 2.

#### 6.5. Baseline

Unless otherwise specified, baseline is defined as the last non-missing measurement taken prior to reference start date (including unscheduled assessments). In absence of unscheduled assessments prior to dosing, the baseline will correspond to Day -1 assessment for physical examination, clinical safety laboratory, 12-lead ECG, PD, CCI measurements; and will correspond to Day 1, Predose assessment for vital signs. In the case where the last non-missing measurement and the reference start date coincide, that measurement will be considered pre-baseline if the assessment is planned per protocol to take place prior to study medication administration. Adverse Events (AEs) and medications commencing on the reference start date will be considered post-baseline unless otherwise indicated based on available start date/time combination or collected electronic Case Report Form (eCRF) data that identifies the

Visterra Insert
Customer Name/ Logo
Protocol VIS954-101
Page 20 of 42

Statistical Analysis Plan

individual event/medication as starting prior to study medication administration.

## 6.6. Retests, Unscheduled Visits and Early Termination Data

In general, for by-visit summaries, data recorded at the nominal visit will be presented. Unscheduled measurements will not be included in by-visit post-baseline summaries but will contribute to the best/ worst-case value where required (e.g., incidence tables for abnormal results by visit and treatment). In the case of a retest (same visit number assigned), the last available measurement for that visit will be used for by-visit summaries.

Early termination data will be mapped to the end of study visit number for by-visit summaries. Listings will include scheduled, unscheduled, retest and early discontinuation data.

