1.3 Schedule of Activities

Table 1.3-1 Sched	ule of As	sessme	ents												
Activity	Screen	Base line		Treatment and Post-treatment Follow-up											
Time Point (Day)	D -28 to D -1	D -1	D 1	D 2	D 3	D5	D 8	D11	D 15	D 22	D 29	D 36	D 43	D 57	D 71 /ET ^a
± Visit Allowance	NA	NA	NA	NA	NA	± 1	+1	± 1	± 3	± 3	± 3	± 3	± 3	± 3	± 3
In-house Stay		X	X	X	X										
Ambulatory Visit	X					X	X	X	X	X	X	X	X	X	X
PROCEDURES															
Informed Consent	X														
Verify Inclusion/ Exclusion Criteria	X	X													
Demographics and Medical History	X														
Pregnancy Test (serum β-hCG) ^b	X														
Pregnancy Test (urine dipstick) ^b		X													X
FSH ^c	X														
Viral Serology	Х														
Urine Drug and Alcohol Screen	X	Х													
Full Physical Examination ^d	X	Х	Xe	X	X										X
Brief Physical Examination ^d							X	X	X						
Vital Signs ^f	X	X	X	X	X	X	X	X	X	X	X	X	X	X	X
12-Lead ECG	X	X		X											
Review of Concomitant Medications								X							
Adverse Events Check								X							
Randomization			X												
Subcutaneous Injection			X												
Assessment of Injection Site ^g			X	X	X						X				

Table 1.3-1 Schedu	ıle of As	sessme	ents												
Activity	Screen	Base line			Treatment and Post-treatment Follow-up										
Time Point (Day)	D -28 to D -1	D -1	D 1	D 2	D 3	D5	D 8	D11	D 15	D 22	D 29	D 36	D 43	D 57	D 71 /ET ^a
± Visit Allowance	NA	NA	NA	NA	NA	± 1	+1	± 1	± 3	± 3	± 3	± 3	± 3	± 3	± 3
Wong-Baker FACES Pain Rating			X	X	X						X				
Scale ^g															
LABORATORY ASSESSMENTS	5														
Hematology	X	X		Xh	X				X		X			X	X
Serum Chemistry and Coagulation	Х	Х		Xh	X				X		X			X	X
Urinalysis	X	Х		Xh	X				X		X			Х	Х
Blood Sampling for PKi, j		Х	X	Х	X	X	Х	X	X	X	X	X	X	Х	X
Blood Sampling for PD (RO)		Х		Xh	X	X	Х	X	X	X	X	X	X		X
Blood Sampling for PD (total leukocytes) ^k		Х		X ^h			Х		Х						

 β -hCG = Beta-human chorionic gonadotropin; D = day; ET =early termination; FSH = follicle stimulating hormone.

Note: Unless otherwise stated, the window allowance for all assessment time points are \pm 15 minutes.

^aIf a participant discontinues from the study, the assessments of the Day 71 visit will be performed at the ET visit.

^bLimited to participants of childbearing potential.

^cLimited to participants in whom nonchildbearing potential needs validation or per trial site standard operating procedure.

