Repeat or unscheduled samples may be taken for safety reasons or for technical issues with the samples.

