8.3.4 Clinical Safety Laboratory Tests

See Section 10.2 for the list of clinical laboratory tests (hematology, serum chemistry, coagulation, and urinalysis) to be performed and the Schedule of Assessments (Table 1.3-1) for the timing and frequency.

An investigator must review the laboratory report, document this review, and record any clinically significant changes occurring during the study as an AE. The laboratory reports must be filed with the source documents.

All laboratory tests with values considered clinically significantly abnormal during participation in the study should be repeated until the values return to normal or baseline or are no longer considered clinically significant by an investigator or medical monitor.

If clinically significant values do not return to normal/baseline within a period of time judged reasonable by the investigator, the etiology should be identified, and the sponsor notified.

All protocol-required laboratory tests, as defined in Section 10.2, must be conducted in accordance with the laboratory manual.

If laboratory values from nonprotocol-specified laboratory tests performed at the institution's local laboratory require a change in participant management or are considered clinically significant by the investigator (eg, SAE or AE or dose modification), then the results must be recorded on the case report form (CRF) or in the electronic case report form (eCRF).

Please see Section 10.5 for guidance on how to assess clinical laboratory parameters with regards to AE intensity.

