## 18.2. Laboratory Evaluations

Results from the local laboratory will be included in the reporting of this study for clinical laboratory analytes in the Hematology, Serum Chemistry and Coagulation, and Urinalysis panels. A list of laboratory assessments to be included in the outputs is included in Appendix 2 of the clinical study protocol, Section 10.2. Presentations will use SI Units.

Quantitative laboratory measurements reported as "< X", i.e., BLQ, or "> X", i.e., above the upper limit of quantification (ULQ), will be converted to X for the purpose of quantitative summaries, but will be presented as recorded, i.e., as "< X" or "> X" in the listings.

The following summaries will be provided for laboratory data:

- Observed and change from baseline by treatment group and visit (for quantitative measurements).
- For participants with both baseline results as well as for the postbaseline visit, shift from baseline
  according to normal range criteria by treatment group and visit (for quantitative measurements and
  categorical measurements)

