## 18.2.2. Toxicity Grading for Laboratory Data

The standardized grading scales based on the FDA Guidance for Industry: Toxicity Grading Scale for Healthy Adult and Adolescent Volunteers Enrolled in Preventative Vaccine Clinical Trials, Sep 2007 are presented in clinical study protocol Section 10.5. Based on these criteria the clinically significant

laboratory test abnormalities assessed as AEs by the principal investigator will be presented in the AE listings.

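### The visible SAP omits the protocol's count of participants with clinically significant laboratory abnormalities, and a repeat coded to the same visit can remove a marked value from both visible laboratory summaries.

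*SAP*

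**What the plan says.** **Retests.** SAP 6.6 sets the rule for a repeat that keeps its visit number: "In the case of a retest (same visit number assigned), the last available measurement for that visit will be used for by-visit summaries". For other extra measurements it says: "Unscheduled measurements will not be included in by-visit post-baseline summaries but will contribute to the best/ worst-case value where required". As an example of the latter it mentions incidence tables of abnormal results. The same section keeps scheduled, unscheduled, retest and early-discontinuation data in the listings.

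**When laboratory tests are repeated.** Protocol 8.3.4: "All laboratory tests with values considered clinically significantly abnormal during participation in the study should be repeated until the values return to normal or baseline". Another stopping point is when an investigator or the medical monitor no longer regards them as clinically significant. The introductory text of protocol section 8 adds: "Repeat or unscheduled samples may be taken for safety reasons or for technical issues with the samples".

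**What is tabulated.** SAP 18.2 names two laboratory summaries. One is observed values and change from baseline by treatment group and visit. The other is a shift from baseline "according to normal range criteria by treatment group and visit". Under SAP 18.2.2, clinically significant "laboratory test abnormalities assessed as AEs by the principal investigator will be presented in the AE" listings. SAP 18.3 and 18.4 each add an incidence table of findings that the investigator judged clinically significant, for ECG and vital signs respectively.

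**What the protocol planned.** Protocol section 9 says that participants with clinically significant abnormalities will be summarized by count and percentage, and laboratory tests are among the domains it names. Protocol 9.2.2.2, the laboratory section, does not repeat this and does not withdraw it. The one readable change in SAP 3.3 concerns the population for disposition.

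**The concern.** Clinical laboratory tests are a primary safety endpoint of this first-in-human study. A reader of the laboratory tables should be able to see, by dose, how many participants had a marked abnormality at any time after dosing. On the visible text two things stand in the way.

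First, the table that would answer the question directly is in the protocol but not in the SAP's laboratory section.

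Second, the tables that remain are by visit, and the retest rule works on exactly those tables. Repeats are prompted by an abnormal result and continue until it resolves, so the last value at a visit tends to be the resolved one. If the repeat carries the visit's number, the value that prompted it leaves both summaries.

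What the tables would lose is the size of the excursion, the visit at which it occurred, and a laboratory-specific participant count by dose.

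**Working it through.** The plan states no figure on this point, so there is nothing to reproduce. The check is textual, with a little arithmetic for scale.

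**1. Does the SAP carry the protocol's count?** The domains in the protocol section 9 sentence, plus ECG for comparison:

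| Domain | Named in that sentence | Visible SAP tabulation |
|---|---|---|
| Vital signs | yes | 18.4: incidence of clinically significant assessments |
| Physical examination | yes | 18.5: shift table of assessments |
| Injection site reactions | yes | 18.1.2: incidence by severity |
| Laboratory tests | yes | 18.2: observed/change and normal-range shift only |
| ECG | no | 18.3: incidence of clinically significant assessments |

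Of the domains named there, laboratory tests alone have no visible tabulation of the investigator's assessment. This holds whether or not any retest occurs.

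**2. Does the retest rule reach the laboratory tables?** Both summaries in SAP 18.2 are by visit, and the 6.6 rule applies to by-visit summaries, so it governs both.
- Repeat coded to the same visit: the last value is used and the scheduled abnormal value is displaced.
- Repeat coded as unscheduled: it stays out of the by-visit summaries and the scheduled value remains.

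Neither document says which coding applies to repeats made under protocol 8.3.4.

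**3. Would another visible laboratory table pick it up?** SAP 6.6 refers to worst-case values where required, but the visible 18.2 requires none. In Table 1.3-1 the row "Serum Chemistry and Coagulation", like those for hematology and urinalysis, has post-dose samples on Days 2, 3, 15, 29, 57 and 71. The gaps are 3 − 2 = 1, 15 − 3 = 12, 29 − 15 = 14, 57 − 29 = 28 and 71 − 57 = 14 days. An excursion that is replaced at its own visit and is normal at the next appears in no visible by-visit laboratory table.

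**4. Scale.** Each cohort randomizes 7 to VIS954 and 2 to placebo; six cohorts give 6 × 2 = 12 pooled placebo participants.
- One participant is 1/7 = 14.3% of a dose group and 1/12 = 8.3% of pooled placebo.
- If one scheduled high value in a dose group is followed by a normal same-visit retest, the shift table reads 0/7 (0%; exact 95% interval 0 to 41.0%). With the scheduled value kept it reads 1/7 (14.3%; 0.4 to 57.9%).

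**5. What it does to the observed-value summary (invented values, illustration only).** Take ALT in multiples of the upper limit of normal: 0.5, 0.6, 0.7, 0.5, 0.8, 0.6 and 3.4, with the last retested at 0.9.
- Mean: 7.1/7 = 1.01 becomes 4.6/7 = 0.66.
- SD: 1.06 becomes 0.15.
- Maximum: 3.4 becomes 0.9.
- Participants above the limit: 1 becomes 0.

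This shows what happens when displacement occurs. It says nothing about how often it would.

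**The case against.** The strongest reply is that little is actually lost. Protocol 8.3.4 tells the investigator to "record any clinically significant changes occurring during the study as an AE", and SAP 18.1.1.2 tabulates unsolicited TEAEs by dose level, with number and percentage of participants, by preferred term and maximum severity. Listings hold every value with its study day. SAP 18.2.2 also closely follows protocol 9.2.2.2, and the protocol promises no worst-value laboratory table. Some repeats are made because a sample failed technically, and there the last value is the sensible one.

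Most of this stands, and it limits the point. A reader might infer that abnormal results vanish from the report; they do not. What remains is narrower. A TEAE table does not give the value, the visit or a laboratory-specific count. A marked value that is repeated, found normal and judged not clinically significant generates no AE and would be seen in the listings only.

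Two other readings go too far. One is that SAP 6.6 shuts same-visit retests out of worst-case values: it mentions only unscheduled measurements there, and silence is not exclusion, so this is an ambiguity to settle. The other is that the rule biases the comparison of drug with placebo. The documents give no laboratory variability, repeat frequency or coding practice, so neither a size nor a direction can be derived.

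Finally, the output templates described in SAP 8 and one item in SAP 3.3 cannot be read here. Either may already contain the missing table or declare the change.

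**Conclusion.** The point holds in a limited form and is worth a modest change. On the visible text, a summary planned in protocol section 9 is missing from SAP 18.2 and its omission is not declared in SAP 3.3. That part does not depend on retests.

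The retest part is conditional. If a repeat under protocol 8.3.4 is given the same visit number, a marked value can drop out of both visible laboratory summaries. Each such case is 14.3% of a dose group of 7. How often this would happen cannot be estimated from the documents.

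The conclusion assumes that the unseen templates and the redacted SAP 3.3 item do not already deal with the matter. Confidence is therefore medium.

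**What to change.** In SAP 18.2 add:

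- the count and percentage of participants with clinically significant laboratory abnormalities, by treatment group, as protocol section 9 plans (if the sponsor intends to drop it, SAP 3.3 should say so);
- a shift from baseline to worst post-baseline value by treatment group, drawing on scheduled, same-visit retest and unscheduled results.

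In SAP 6.6 state that the original and the retest value at a visit both contribute to worst-case values. Leave the general last-value rule for by-visit summaries as it is: it also serves ECG and vital signs, and the worst-value table meets the laboratory concern without changing it.

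The cost is a few sentences and one or two tables from data already collected. The drawback is that a spurious first value that was never invalidated would be shown. If the templates already include these outputs, a confirming sentence in 18.2 and the 6.6 clarification are enough.
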